2.4 Schedule of Assessments

Table 1 below presents the schedule of assessments.

Table 1 Schedule of Assessments

| Procedure (All ocular assessments and procedures performed bilaterally) | Visit 1 Screening ^a and Baseline (Day 1) -1 Day | Visit 2 (Day 3) +1 Day | Visit 3 (Day 5) | Visit 4 (Day 8) +1 Day | Visit 5 ^b (Day 12) +2 Days |
|---|--|------------------------------|--------------------|------------------------------|---|
| Informed consent/assent ^a | X | | | | |
| Inclusion/exclusion criteria ^a | X | | | | |
| Medical history | X | | | | |
| Demographics | X | | | | |
| Concomitant medications | X | X | X | X | X |
| Urine pregnancy test | X ^c | | | | X ^c |
| Ocular discomfort scale | X | X | X | X | X |
| Best corrected visual acuity | X | X | X | X | X |
| Slit lamp biomicroscopy | X | X | X | X | X |
| Bulbar conjunctival injection evaluation | X | X | X | X | X |
| Ocular conjunctival discharge evaluation | X | X | X | X | X |
| AdenoPlus [®] test | X ^d | | | | |
| Conjunctival swab for bacterial culture ^e | X | X ^f | X ^f | X ^f | X |
| Conjunctival swab to test for HSV, and chlamydia and gonorrhea ^l | X | | | | |
| Non-dilated/dilated fundus examination ^k | X | | | | X |
| Randomization ^g | X | | | | |
| Dispense investigational product ^h | X | | | | |
| Instill investigational product | X ^h | X ⁱ | X ⁱ | | |
| Collect investigational product | | | | X | X ^b |
| Compliance assessment | | X | X | X | X ^b |
| Drug accountability | | | | X | X ^b |
| Adverse events | X ^j | X | X | X | X |
| Study completion | | | | | X |

ET=early termination;

^a Informed consent and confirmation of inclusion/exclusion criteria can be conducted on Day -1; these criteria must be reconfirmed on Day 1.

^b If investigational product is discontinued, regardless of the reason, all discontinued subjects should proceed to Visit 5 whenever possible. Subjects who discontinue the study and proceed to Visit 5 should perform all Visit 5 assessments as well as drug return, compliance, and accountability.

^c Women of childbearing potential, prior to enrollment and at exit from the study

^d If not previously conducted within 24 hours of Visit 1 (Day 1)

^e One swab sample from inferior conjunctival cul-de-sac of each eye will be collected for all bacterial testing.

^f Conjunctival swab samples MUST be taken at least 12 hours after the last dose of investigational product at Visits 2, 3, 4, and ET, if applicable.

^g All assessments, randomization, and investigational product instillation on Day 1 must take place with sufficient time to allow

Table 1 Schedule of Assessments

| Procedure (All ocular assessments and procedures performed bilaterally) | Visit 1 Screening ^a and Baseline (Day 1) -1 Day | Visit 2 (Day 3) +1 Day | Visit 3 (Day 5) | Visit 4 (Day 8) +1 Day | Visit 5 ^b (Day 12) +2 Days |
|--|--|------------------------------|--------------------|------------------------------|---|
|--|--|------------------------------|--------------------|------------------------------|---|

all 4 Day 1 doses (with a minimum of 2 hours between doses).

^h The investigational product bottle should be shaken well prior to use at each dosing. The first dose will be administered by site staff on Day 1, and thereafter subjects will administer 1 drop in each eye 4 times a day for 7 days.

ⁱ Investigational product instillation should only be performed in-office if it is necessary.

^j Monitoring for adverse events will begin after informed consent is obtained.

^k If a non-dilated fundus exam is not feasible, a dilated examination should be conducted. For each subject, the exam should be conducted the same way (either non-dilated or dilated) at both Visits 1 and 5 (or ET).

^l This sample will be used for baseline HSV testing for all subjects. For subjects <2 months of age, testing for chlamydia and gonorrhea detection will also be conducted using the same sample.

2.5 Determination of Sample Size

The sample size was estimated for the primary comparison of SHP640 versus placebo on clinical resolution in the treatment of subjects with bacterial conjunctivitis in the study eye at Visit 3 (Day 5) using nQuery Advisor 7.0. Subjects will be randomized 3:1:3 to receive either SHP640, PVP-I, or placebo within each age stratum.

The primary efficacy endpoint is clinical resolution status (defined as absence [ie, a score of 0] of bulbar conjunctival injection and ocular conjunctival discharge) in the study eye at Visit 3 (Day 5) between SHP640 and placebo. The null hypothesis to be tested is that there is no difference in proportion of subjects with clinical resolution in the study eye between SHP640 ophthalmic suspension and placebo with the alternative of the non-zero difference in the proportion with clinical resolution between them.

A sample size of 504 subjects (216 subjects in each of the SHP640 and placebo groups, 72 in PVP-I group) will ensure ~90% power to compare the SHP640 and placebo treatment groups assuming 61% and 45% subjects with clinical resolution, respectively, using Fisher's Exact test at 2-sided 5% level of significance.

All efficacy analyses will be based on the modified Intent-to-Treat (mITT) population (refer to Section 4.4 for the definition of mITT) with post-baseline last observation carried forward (LOCF) for the subjects with missing clinical resolution status at Visit 3 (Day 5). To ensure 504 subjects in the mITT population, approximately 721 subjects will be randomized in this study (approximately 309 subjects in each of SHP640 and placebo groups; approximately 103 subjects in PVP-I group).

2.6 Multiplicity Adjustments for Type I Error Control

An unmasked interim analysis (IA) will be performed after ~50% subjects exit the trial in the mITT population for possible sample size increase. The final sample size will be calculated in the unmasked IA based on the conditional power for the primary comparison of SHP640 versus placebo on clinical resolution in the treatment of subjects with bacterial conjunctivitis in the

study eye at Visit 3 (Day 5). There is no inflation of type I error from this IA because the sole purpose of the IA is to adjust the sample size by using the conditional power approach, and the sample size will be changed only under certain conditions (Mehta and Pocock, 2011). However, for conservativeness, two sided 0.0001 alpha will be spent for the proposed IA and a two sided alpha of 0.0499 will be used for final analyses.

Formal hypothesis testing will be conducted on the primary efficacy endpoint and key secondary efficacy endpoint with a total of 2 pairwise comparisons. The comparison on the primary efficacy endpoint will be based on clinical resolution in the study eye at Visit 3 (Day 5) between SHP640 and placebo in the mITT population. The comparison on the key secondary efficacy endpoint will be based on bacterial eradication in the study eye at Visit 3 (Day 5) between SHP640 and placebo in the mITT population.

A fixed sequence procedure will be used to maintain the study-wide Type I error at 4.99% for final analyses with the primary efficacy endpoint being tested first and the key secondary efficacy endpoint being tested second. Both the primary and key secondary hypothesis tests will be conducted at the two-sided 0.0499 significance level following the pre-specified order. The hypothesis test for the key secondary efficacy endpoint will not be performed unless the hypothesis test for the primary efficacy endpoint is statistically significant.

3. OBJECTIVES

3.1 Primary Objective

The primary objective of this study is to evaluate the efficacy of SHP640 based on clinical resolution (defined as absence of bulbar conjunctival injection and ocular conjunctival discharge) compared with placebo in the treatment of subjects with bacterial conjunctivitis in the study eye at Visit 3 (Day 5).

3.2 Secondary Objective

The key secondary objective is to evaluate the efficacy of SHP640 based on bacterial eradication (defined as absence of all bacterial species present at or above pathological threshold at baseline) compared with placebo in the treatment of subjects with bacterial conjunctivitis in the study eye at Visit 3 (Day 5).

Other secondary objectives of this study are as follows:

- To evaluate the effect of treatment in the study eye, for the following endpoints:
 - Clinical resolution of bacterial conjunctivitis at Visits 2 (Day 3), 4 (Day 8), and 5 (Day 12)
 - Bacterial eradication at Visits 2 (Day 3), 4 (Day 8), and 5 (Day 12)
 - Absolute and change from baseline of the individual clinical signs (bulbar conjunctival injection and ocular conjunctival discharge) at Visits 2 (Day 3), 3 (Day 5), 4 (Day 8), and 5 (Day 12)
 - The global clinical score (sum of bulbar conjunctival injection and ocular conjunctival discharge) and change from baseline in the global clinical score at Visits 2 (Day 3), 3 (Day 5), 4 (Day 8), and 5 (Day 12)
 - Modified clinical resolution, defined as a global clinical score of 0 or 1, at Visits 2 (Day 3), 3 (Day 5), 4 (Day 8), and 5 (Day 12)
 - Expanded clinical resolution, defined as a global clinical score of 0, 1, or 2 with neither injection nor discharge having a score of 2, at Visits 2 (Day 3), 3 (Day 5), 4 (Day 8), and 5 (Day 12)
 - Time to clinical resolution based upon assessments at Visits 2 (Day 3), 3 (Day 5), 4 (Day 8), and 5 (Day 12)
- To evaluate the safety and tolerability of SHP640, compared to PVP-I and placebo in the treatment of subjects with bacterial conjunctivitis
- Use of rescue medication

3.3 Exploratory Objective

The exploratory objective of this study is as follows:

- To evaluate ocular discomfort due to conjunctivitis symptoms in subjects receiving SHP640 compared to PVP-I and placebo at Visits 2 (Day 3), 3 (Day 5), 4 (Day 8), and 5 (Day 12)

4. SUBJECT POPULATION SETS

4.1 Screened Population

The Screened Population will consist of all subjects who have provided written informed consent.

4.2 Safety Population

The Safety Population will consist of all subjects who receive at least one dose of investigational product.

4.3 Intent to Treat (ITT) Population

The Intent-to-Treat (ITT) Population will include all randomized subjects.

4.4 Modified Intent to Treat (mITT) population

The mITT Population consists of a subset of the ITT population who receive at least one dose of investigational product and have a positive bacterial culture (presence of one or more bacterial species at or above pathological threshold) at baseline (i.e. Visit 1) in the study eye.

Pathological threshold for individual bacterial species will be based on colony forming unit (CFU)/ml threshold levels established by Cagle and modified by Leibowitz ([Leibowitz, 1991](#)) for different ocular bacterial species found in the specimens collected from each subject as specified in Appendix [20.1](#).

5. SUBJECT DISPOSITION

A listing of all Screen Failures (ie, subjects who were screened but not randomized) will be presented along with reasons for screen fail.

The number of subjects included in each subject population (ie, Screened, Safety, ITT and mITT) will be summarized by randomized treatment group, age strata and overall except for the Screened Set, which will be summarized for all subjects only.

The number and percentage of subjects who completed and prematurely discontinued during the Double-masked Evaluation Phase will be presented for each treatment group, age strata and overall. Reasons for premature discontinuation from the Double-masked Evaluation Phase as recorded on the termination page of the eCRF will be summarized (number and percentage) by treatment group, age strata and overall. All percentages will be based on the number of subjects in the ITT Population.

A listing of disposition will be provided for all subjects. All subjects who prematurely discontinued during the Double-masked Evaluation Phase will be listed by discontinuation reason.

6. PROTOCOL DEVIATIONS

Protocol deviations will be recorded by the site monitors separately from the clinical database. Protocol deviations will be listed and summarized for subjects in the ITT Population for each treatment group by country and overall. Summary tables will be presented with the following Clinical Trial Management System (CTMS) categories:

- Informed Consent
- Eligibility and Entry Criteria
- Concomitant Medication Criteria
- Laboratory Assessment Criteria
- Study Procedures Criteria
- Serious Adverse Event Criteria
- Randomization Criteria
- Visit Schedule Criteria
- IP Compliance
- Efficacy Criteria
- Administrative Criteria
- Source Document Criteria
- Regulatory or Ethics Approvals Criteria
- Other Criteria

In addition to the 14 CTMS categories, number of subjects in the ITT population for each treatment group by country and overall will also be summarized for subjects coming to visits who did not have 12 hours since their last dose, which could be mapped to multiple CTMS categories.

7. DEMOGRAPHIC AND OTHER BASELINE CHARACTERISTICS

Descriptive summaries of demographic and baseline characteristics will be presented by treatment group and overall for ITT and mITT.

The following demographic characteristics will be summarized in the following order in the tables: age, age strata (< 6 years [0-27 days], 6 to <18 years and \geq 18 years), sex, ethnicity and race. In addition, iris color in the study eye will be summarized.

Percentages will be based on the total number of subjects in each treatment group.

A listing will be generated for demographic and baseline characteristics for the ITT Population.

Ocular and non-ocular medical history will be descriptively summarized based on the system organ class (SOC) and preferred term coded terms (Medical Dictionary for Regulatory Activities [MedDRA] version 19.1) by treatment group and overall for the Safety Population. Data summaries will be sorted by the overall frequency of reporting within SOC.

A listing of ocular and non-ocular medical history will be provided for the Safety Population.

8. EXTENT OF EXPOSURE AND TREATMENT COMPLIANCE

8.1 Exposure to Investigational product

Exposure to double-masked investigational product for the Safety Population will be summarized in terms of treatment duration, which is calculated as the number of days from the date of first dose of double-masked investigational product taken to the date of the last dose of double-masked investigational product taken, inclusively, and irrespective of any investigational product interruption(s). Descriptive statistics will be presented by treatment group and overall.

A listing of investigational product exposure will be provided for all subjects in the Safety Population.

8.2 Measurement of Treatment Compliance

Investigational product dosing compliance for the double masked treatment period is defined as the total number of doses actually taken by a subject during that period divided by the number of doses expected to be taken during the same period multiplied by 100.

For completers (i.e. subjects who completed all 7 days of dosing), the total number of expected doses is 28 (i.e. 4 doses per day for 7 days). For subjects who early terminated dosing on Day 1, the total number of expected doses is set to be 1. For the rest of subjects who terminated dosing before 7 days, the total number of expected doses is the number of full dosing day multiplied by 4. For example, if a subject early terminates on Day 4, his/her total number of expected doses is 3 (full dosing day) x 4 (doses per day) = 12.

At each visit, the number of missed doses or extra doses since last visit will be recorded on the CRF. The total number of missed doses will be derived as the sum of the number of missed doses since last visit across all visits. The total number of extra doses will be derived as the sum of the number of extra doses since last visit across all visits. The total number of doses actually taken will be derived as the total number of expected doses plus the total number of extra doses minus the total number of missed doses.

Descriptive statistics [number of subjects (n), mean, median, standard deviation (SD), minimum, maximum] for investigational product compliance will be presented by treatment group and overall for the whole double-masked evaluation phase for the Safety Population. Number of subjects (percentage) who completed 4 days of dosing by Visit 3 with no extra or missed dose will also be presented by treatment group and overall for the Safety Population.

A listing of treatment compliance will be provided for all subjects in the Safety Population.

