Procedure (All ocular assessments and procedures performed bilaterally)	Visit 1 Screening ^a and Baseline (Day 1) -1 Day	Visit 2 (Day 3) +1 Day	Visit 3 (Day 5)	Visit 4 (Day 8) +1 Day	Visit 5 ^b (Day 12) +2 Days
Informed consent/assent ^a	X				
Inclusion/exclusion criteria ^a	X				
Medical history	X				
Demographics	X				
Concomitant medications	X	X	X	X	X
Urine pregnancy test	X ^c				X ^c
Ocular discomfort scale	X	X	X	X	X
Best corrected visual acuity	X	X	X	X	X
Slit lamp biomicroscopy	X	X	X	X	X
Bulbar conjunctival injection evaluation	X	X	X	X	X
Ocular conjunctival discharge evaluation	X	X	X	X	X
AdenoPlus [®] test	X ^d				
Conjunctival swab for bacterial culture ^e	X	X ^f	X ^f	X ^f	X
Conjunctival swab to test for HSV, and chlamydia and gonorrhea ^l	X				
Non-dilated/dilated fundus examination ^k	X				X
Randomization ^g	X				
Dispense investigational product ^h	X				
Instill investigational product	X ^h	X ⁱ	X ⁱ		
Collect investigational product				X	X ^b
Compliance assessment		X	X	X	X ^b
Drug accountability				X	X ^b

Table 1 Schedule of Assessments

Procedure (All ocular assessments and procedures performed bilaterally)	Visit 1 Screening^a and Baseline (Day 1) -1 Day	Visit 2 (Day 3) +1 Day	Visit 3 (Day 5)	Visit 4 (Day 8) +1 Day	Visit 5^b (Day 12) +2 Days
Adverse events	X ^j	X	X	X	X
Study completion					X

ET=early termination;

^a Informed consent and confirmation of inclusion/exclusion criteria can be conducted on Day -1; these criteria must be reconfirmed on Day 1.

^b If investigational product is discontinued, regardless of the reason, all discontinued subjects should proceed to Visit 5 whenever possible. Subjects who discontinue the study and proceed to Visit 5 should perform all Visit 5 assessments as well as drug return, compliance, and accountability.

^c Women of childbearing potential, prior to enrollment and at exit from the study

^d If not previously conducted within 24 hours of Visit 1 (Day 1)

^e One swab sample from inferior conjunctival cul-de-sac of each eye will be collected for all bacterial testing.

^f Conjunctival swab samples MUST be taken at least 12 hours after the last dose of investigational product at Visits 2, 3, 4, and ET, if applicable.

^g All assessments, randomization, and investigational product instillation on Day 1 must take place with sufficient time to allow all 4 Day 1 doses (with a minimum of 2 hours between doses).

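### For subjects who stop early, the SAP 8.2 dose count leaves out the stopping day but subtracts missed doses from every visit, so compliance can be wrong and sometimes negative

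*SAP*

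**What the plan says.** SAP 8.2 defines compliance as doses actually taken "divided by the number of doses expected to be taken during the same period multiplied by 100". Three rules set the expected number:

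- Completers: 28 doses.
- Day 1 stops: "For subjects who early terminated dosing on Day 1, the total number of expected doses is set to be 1".
- All other early stops: "the total number of expected doses is the number of full dosing day multiplied by 4". In the worked example of a Day 4 stop, "his/her total number of expected doses is 3 (full dosing day) x 4 (doses per day) = 12".

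The number taken is not observed. It is "derived as the total number of expected doses plus the total number of extra doses minus the total number of missed doses". For the last term, "The total number of missed doses will be derived as the sum of the number of missed doses since last visit across all visits". Nothing restricts that sum to the days in the expected count, nothing adds back doses taken on the stopping day, and no lower bound is given.

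The result is summarised for the Safety Population, which under SAP 4.2 contains only subjects with at least one dose. It goes into Table 14.3.8.2 and Listing 16.2.5.3. On Day 1, the footnotes to Protocol Table 1 say that procedures "must take place with sufficient time to allow all 4 Day 1 doses (with a minimum of 2 hours between doses".

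**The concern.** Subtracting missed from expected recovers doses taken only if both are counted over the same days, which the section's own definition requires. For early stoppers they are not. The expected count ends with the last full day, or after one dose on Day 1, while missed doses run on through the stopping day and possibly beyond. Doses taken on the stopping day appear in neither term.

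The compliance percentage is the planned dose-based measure of how fully product was used. A reader would consult it to see whether subjects who stopped were taking their drops until then. Section 8.2 reports mean, SD and minimum, so an impossible value would enter the table directly.

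**Working it through.** **Notation.** E is the SAP's expected count: 28 for completers, 1 for a Day 1 stop, otherwise 4 × (stopping day - 1). L is the number of doses scheduled from the first dose up to and including the last dose taken. m is missed doses and x is extra doses.

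- SAP doses taken = E + x - m; SAP compliance = 100 × (E + x - m)/E.
- With one common span: doses taken = L + x - m; compliance = 100 × (L + x - m)/L.

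**The plan's own figures reproduce.** Completers: 4 × 7 = 28. Day 4 stop: 4 × 3 = 12.

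**Size of the count error.** If only misses before the last dose are recorded, and x = 0, the SAP count minus the true count is (E - m) - (L - m) = E - L. The shortfall is therefore the number of scheduled doses on the stopping day up to the last dose. For a Day 1 stop it is that number minus one. It is zero if the last dose was the evening before, or was the single first dose on Day 1.

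**Cases that need no assumption about doses after stopping:**

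| Subject | E | m | SAP taken | SAP compliance | L | True taken | Common-span compliance |
|---|---|---|---|---|---|---|---|
| Stops Day 4 after 3 doses that day, none missed | 12 | 0 | 12 | 100% | 15 | 15 | 100% |
| Same, with 2 missed on Days 1-3 | 12 | 2 | 10 | 83.3% | 15 | 13 | 86.7% |
| Stops Day 1 after 4 doses | 1 | 0 | 1 | 100% | 4 | 4 | 100% |
| Day 1: takes first, misses one, takes third, stops | 1 | 1 | 0 | 0% | 3 | 2 | 66.7% |
| Day 1: takes first, misses two, takes fourth, stops | 1 | 2 | -1 | -100% | 4 | 2 | 50% |

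With no missed doses the percentage is right and only the underlying count is wrong. With missed doses before the last dose and L above E, the percentage is wrong as well. Zero or negative counts contradict the Safety Population definition.

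**How low it can go on this basis.** The extreme is a subject who takes only the first dose and the last slot of the stopping day. Then L = E + 4, m = E + 2, and the SAP count is -2. For a Day 2 stop that is -2/4 = -50%; for a Day 3 stop, -2/8 = -25%. These need almost complete non-use, so for stops after Day 1 ordinary errors are a few percentage points.

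**Cases that depend on how the CRF is completed, which the documents do not show:**

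- Stops Day 1 after the first dose, the other three recorded as missed: 1 - 3 = -2, or -200%. Common span: 1/1.
- Stops Day 4 after one dose that day, every untaken dose to Day 7 recorded as missed: m = 28 - 13 = 15, so 12 - 15 = -3 and -3/12 = -25%. Common span: 13/13.
- Takes two doses on Day 1 and stops, the second entered as extra: 1 + 1 = 2, or 200%. Common span: 2/2.

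**The case against.** The best defence is that the full-day rule suits stops at scheduled visits. Protocol 7.1.2 tells subjects not to dose in the 12 hours before a visit, so someone stopped at Visit 2, 3 or 4 would normally have taken nothing that day and nothing is lost. That stands for those subjects, provided the withheld doses are not entered as missed. It does not cover stops between visits, or Day 1 stops.

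A second defence is that large negative values need unusual dosing patterns, or post-stop doses recorded as missed. Protocol 4.4 and 7.1.3 send discontinued subjects to Visit 5 procedures, for rescue at the time of discontinuation, and no CRF instruction shown calls later doses missed. This stands as a limit on frequency. The rule still produces the Day 1 result without any such convention.

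Three stronger readings are tempting, and the documents do not support them:

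- A reader might infer that early stopping becomes invisible, or that one arm's intolerance would be hidden. It would not. SAP 8.1 summarises treatment duration (Table 14.3.8.1), SAP 5 tabulates discontinuation and reasons, and SAP 11.1 tabulates adverse events leading to discontinuation. SAP 8.2 also reports how many subjects completed four days of dosing by Visit 3 with none missed or extra, a figure that does not use the disputed formula.
- A reader might object that an early stopper can score 100%. Measuring compliance only while on treatment is a legitimate definition, and the repaired rule does the same. The fault is the mismatch of spans.
- A reader might infer that doses could simply be counted from instillation records. SAP 8.2 says the CRF holds missed and extra doses since the last visit, and Protocol 6.5 has compliance checked verbally. Listing 16.2.5.2 is only a title, so home-dose counts are not shown to exist.

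**Conclusion.** The concern holds as a rule that conflicts with its own definition. For early stoppers, doses taken on the stopping day are lost from the count (12 instead of 15 in the Day 4 example). Compliance is wrong when such a subject also has missed doses (83.3% instead of 86.7%), and a Day 1 stop can give -100% where 50% is correct. For later stops, negative values require near-total non-use or post-stop doses recorded as missed.

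The scope is narrow. Completers are unaffected, as are subjects whose last dose was the evening before termination with no later misses recorded. The effect is confined to Table 14.3.8.2 and Listing 16.2.5.3. No efficacy test, analysis population or treatment-duration figure uses the count. How many subjects would be affected cannot be judged from the documents. The correction is worth making because it is cheap and removes impossible values; it does not threaten the trial's conclusions.

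**What to change.** Amend SAP 8.2 before unmasking so that expected, extra and missed doses all refer to one span: first dose to last dose, including the stopping day up to that dose. Treat Day 1 stops the same way instead of fixing them at one. State that doses after the last dose taken are not missed doses, and that scheduled doses taken on the stopping day are not extra doses.

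Derive this from the missed and extra counts and the last-dose date already collected. The sponsor should confirm which stopping-day data exist. SAP 10.5 already needs the interval between last dose and swab, so some last-dose timing should be available. No floor at zero is needed: once the spans match, every subject in the table has at least one dose counted.

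Optionally, add compliance against the planned 28 doses as a supplementary descriptive line. The cost is a few sentences and minor reprogramming of one table and one listing.
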